7.5 Follow-up Procedures for Participants Who Permanently Discontinue Study Product

7.5.1 Participants Who Become Infected with HIV-1/2

If a participant tests positive for HIV-1/2 after the Enrollment Visit, he/she will be referred to local care and treatment services and may return to the research clinic for additional counseling and other support services, as needed. Continued study participation would be of no added benefit, thus follow-up visits will be discontinued and the participant will be considered terminated from the study. An Early Termination Visit (please refer to the MTN-037 SSP Manual for specific procedures) will be conducted, if the participant is willing. Participants who seroconvert after enrollment may be offered additional laboratory testing (such as HIV RNA and HIV drug resistance testing), as clinically indicated, per discussions between the site IoR and LC. Please reference the MTN-037 SSP Manual for additional details (www.mtnstopshiv.org).

7.5.2 Participants Who Become Pregnant

If a participant becomes pregnant, she will be referred to local health care services and may return to the research clinic for additional counseling, as needed. Continued study participation would be of no added benefit to the participant, thus follow-up visits will be discontinued and the participant will be considered terminated from the study. An Early Termination Visit will be conducted, if the participant is willing. A participant who is pregnant at study termination will continue to be followed until the pregnancy outcome is ascertained, see Section 9.6 for additional details.

Participants who become pregnant while on study product will be offered enrollment in MTN-016 (www.mtnstopshiv.org) which includes follow-up throughout the pregnancy and for the first year of the infant's life. Additionally, for participants who choose not to enroll in MTN-016, the study site will make every reasonable effort to contact participants and collect infant outcome at approximately one year after delivery for those pregnancies that result in live birth. For additional details regarding obtaining pregnancy and infant outcomes, please reference the MTN-037 SSP Manual (www.mtnstopshiv.org).

7.5.3 Participants Who Permanently Discontinue Study Product for Other Reasons

Participants who permanently discontinue study product use for any reason (clinician-initiated or self-initiated) will be considered terminated from the study and the PSRT should be notified. Continued study participation would be of no added benefit, thus follow-up visits will be discontinued and the participant will be considered terminated from the study. An Early Termination Visit will be conducted, if the participant is willing. Participants who permanently discontinue study product use due to an AE must continue to be followed off-study until resolution or stabilization of the AE is documented.

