7.4 Follow-up Visits

7.4.1 Dosing – Visits 3, 5, and 7

The first dosing on Visit 3 should occur approximately 14 days after the Enrollment Visit.

After a two-to-six-week washout period (to accommodate scheduling around the menstrual cycles of female participants) following each dosing visit, participants will return to the clinic for assessment. If no adverse events (AEs) that preclude continuation to the next dose are identified (based on product hold criteria in Section 9 and discretion of the loR/designee), participants will receive the next scheduled dose of the study gel. Please see the SSP Manual for additional information.

All participants will undergo PK and PD assessments within 24 hours after each gel administration. Participants will be randomized 1:1:1:1 to one of the following 4 time frames to provide samples of rectal tissue, rectal fluid, vaginal fluid (if applicable), and effluent from rectal lavage: 0.5-1 hour, 1.5-3 hours, 3.5-5 hours, and 24 hours following PC-1005 gel application. This time frame will remain consistent across gel volumes.. Procedures for the day of dosing are listed in

Table 13 below.

Table 13: Dosing Procedures

able 1	3: Dosing Procedures	ing Dunnadanan Maita O. F. and 7	
	Dosing Procedures – Visits 3 , 5, and 7 Component Procedures		
	Component		
Admi	inistrative and Regulatory	Noview aparte locater information	
		Provide reimbursement	
		Schedule next visit/contact	
Е	Behavioral/Counseling	Protocol counseling	
		Behavioral assessment	
		Review/update medical history	
		 Perform targeted physical examination* 	
		Perform male genital examination*	
		Perform pelvic examination*	
	Clinical	Perform rectal examination	
		Review/update concomitant medications	
		Treat or prescribe treatment for RTI/UTI, or STIs*	
		Disclose available test results	
		Record/update AEs	
	Pharyngeal	NAAT for GC/CT*	
		NAAT for GC/CT*	
	Urine	Urine dipstick/culture*	
		Qualitative hCG ♀	
		CBC with differential and platelets*	
حَ	Blood	Chemistries (Creatinine only)	
ato	2.000	Syphilis serology*	
Laboratory		Blood for PK ■ Blood fo	
La	Pelvic	Vaginal fluid for PK△♀	
		NAAT for GC/CT/TV*♀	
		Rectal enema effluent for PD prior to biopsy collection ∴	
	Anorectal	Rectal fluid for PK and PD	
	Allolottal	Rectal tissue for PK, PD, histology, and archive	
		HSV 1/2 detection*	
		NAAT for GC/CT*	
S	tudy Product/Supplies	Administration of study product	
		Offer condoms	

^{*} If indicated. ♀Female participants.

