☆ Please reference the MTN-037 SSP Manual for additional details (www.mtnstopshiv.org)

▲ Participants will receive a single dose of study product (4 mL, 16 mL, or 32 mL) depending on dosing visit.

△= Participants will be randomized 1:1:1:1 to provide samples of rectal tissue, rectal fluid, vaginal fluid (if applicable), and effluent from rectal lavage in one of the following time periods after dose administration across gel volumes: 0.5-1 hour; 1.5-3 hours; 3.5-5 hours, or 24 hours. (Those assigned to the 24 hour time point to provide samples will do so at the 24-hr Post-dose visit instead of the Dosing visit).

♦ Blood will be collected pre-dose administration and at 1 hour, 2 hours, 3 hours, 4, hours, 5-6 hours and 24 hours after dose administration

NOTE: Participants will be instructed to call in to the clinic to report any issues related to the collection of samples via the flexible sigmoidoscopy. See SSP Manual for additional details.

7.4.2 24-Hour Post-Dosing Visits

Safety laboratory tests and blood for PK will be collected from all participants at the 24 hour post-dosing visit. Additionally, participants randomized to sample collection at 24 hours will have PK and PD samples collected.

Table 14: 24-Hour Post-Dosing Visits

usio 141 2	24-Hour Post-Dosing Visits - Visits 4, 6, and 8		
	Component	Procedures	
Administrative and Regulatory		 Review/update locator information Provide reimbursement Schedule next visit/contact π 	
Behavioral/Counseling		 HIV pre- and post-test counseling (Visit 8 only) HIV/STI risk reduction counseling (Visit 8 only) Protocol counseling IDI (Visit 8 only) 	
	Clinical	 Review/update medical history Perform targeted physical examination* Perform male genital examination* Perform pelvic examination* Perform rectal examination Review/update concomitant medications Treat or prescribe treatment for RTI/UTI, or STIs* Disclose available test results Record/update AEs 	
	Pharyngeal	NAAT for GC/CT*	
	Urine	 NAAT for GC/CT* Urine dipstick/culture* 	
Laboratory	Blood	 CBC with differential and platelets Chemistries (AST/ALT/Creatinine) Syphilis serology* HIV-1/2 test (Visit 8 only) Blood for PK◆π 	
	Pelvic	Vaginal fluid for PK△♀ NAAT for GC/CT/TV*♀	

	24-Hour Post-Dosing Visits - Visits 4, 6, and 8			
Component		Procedures		
		Anal swab for HPV		
		 Rectal enema effluent for PD prior to biopsy collection		
	Anorectal	Rectal fluid for PK and PD△π		
		 Rectal tissue for PK, PD, histology, and archive		
		HSV 1/2 detection*		

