		NAAT for GC/CT*		

^{*} If indicated. ♀ Female participants.

NOTE: Participants will be instructed to call in to the clinic to report any issues related to the collection of samples via the flexible sigmoidoscopy. See SSP Manual for additional details.

7.4.3 48-Hour Post-Dosing Visits

Participants will be randomly assigned 1:1:1 to provide samples of blood, rectal tissue, rectal fluid, vaginal fluid (if applicable), and effluent from rectal lavage samples 48 hours following PC-1005 administration for one of the 3 gel volume levels (4 mL, 16 mL, or 32 mL). Participants will only attend one 48-hour visit during the study.

Table 15: 48-Hour Post-Dosing Visits

48-Hour Post-Dosing Visits - Visits 4a, 6a, and 8a			
	Component	Procedures	
Adminic	strative and Begulatory	Review/update locator information	
Adminis	strative and Regulatory	Provide reimbursement	
		Schedule next visit/contact	
Beh	avioral/Counseling	Protocol counseling	
		Review/update medical history	
		 Perform targeted physical examination* 	
		 Perform male genital examination* 	
		 Perform pelvic examination*	
	Clinical	Perform rectal examination	
		 Review/update concomitant medications 	
		 Treat or prescribe treatment for RTI/UTI, or STIs* 	
		Disclose available test results	
		Record/update AEs	
rat	Pharyngeal	NAAT for GC/CT*	
Laborat	Urine	Urine dipstick/culture*	
La		NAAT for GC/CT*	

π Please reference the MTN-037 SSP Manual for additional details (www.mtnstopshiv.org) regarding the appropriate procedures to complete for an Early Termination Visit.

^{△=} Participants will be randomized 1:1:1:1 to provide samples of rectal tissue, rectal fluid, vaginal fluid (if applicable), and effluent from rectal lavagein one of the following time periods after dose administration across gel volumes: 0.5-1 hour; 1.5-3 hours; 3.5-5 hours, or 24 hours. (Those assigned to the 24 hour time point to provide samples will do so at the 24-hr Post-dose visit instead of the Dosing visit).

^{♦=} Blood will be collected pre-dose administration and at 1 hour, 2 hours, 3 hours, 4, hours, 5-6 hours and 24 hours after dose administration

48-Hour Post-Dosing Visits - Visits 4a, 6a, and 8a		
Component	Procedures	
Blood	 Blood for PK Chemistries (AST/ALT/Creatinine)* CBC with differential and platelets* Syphilis serology* 	
Pelvic	Vaginal fluid for PK♀ NAAT for GC/CT/TV*♀	

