7.4.4 Final Contact

The *Final Contact* (Visit 9) will occur either in-person or by phone approximately two to six weeks after the third dosing visit (32 mL) of PC-1005 gel application. This contact will also serve as the participant's study termination.

Table 16: Final Contact

Final Contact – Visit 9			
Component	Procedures		
Administrative and Regulatory	 Review/update locator information Provide reimbursement ~ Schedule next visit/contact* 		
Behavioral/Counseling	 HIV pre- and post-test counseling* HIV/STI risk reduction counseling* Protocol counseling* 		
Clinical	 Review/update medical history Perform targeted physical examination* Perform male genital examination* Perform pelvic examination* Perform rectal examination* Review/update concomitant medications Treat or prescribe treatment for RTI/UTI, or STIs* Disclose available test results Record/update AEs 		
্ৰ Pharyngeal	NAAT for GC/CT*		

Please reference the MTN-037 SSP Manual for additional details (www.mtnstopshiv.org)

	Final Contact – Visit 9		
	Component	Procedures	
		NAAT for GC/CT*	
	Urine	Urine dipstick/culture*	
		Qualitative hCG* ♀	
		CBC with differential and platelets*	
	Blood	Chemistries (AST/ALT/Creatinine)*	
	Biood	Syphilis serology*	
		HIV-1/2 test*	
Study Product/Supplies		Offer condoms*	

^{*} If indicated. ♀ Female participants. ~ Sites to reference SOPs regarding participant reimbursement.

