8.3 Adverse Events Definitions and Reporting Requirements

8.3.1 Adverse Events

An AE is defined as any untoward medical occurrence in a clinical research participant administered an investigational product and which does not necessarily have a causal relationship with the investigational product. As such, an AE can be an unfavorable or unintended sign (including an abnormal laboratory finding, for example), symptom or disease temporally associated with the use of an investigational product, whether or not considered related to the product. This definition is applied to all study groups, and is applied to all groups beginning at the time of enrollment through the termination visit. The term "investigational product" for this study refers to PC-1005 (0.002% MIV-150/0.3% Zinc acetate [ZA] in 3.0% Carrageenan [CG] gel).

Study participants will be provided instructions for contacting the study site to report any untoward medical occurrences they may experience. In cases of potentially lifethreatening events, participants will be instructed to seek immediate emergency care. Where feasible and medically appropriate, participants will be encouraged to seek evaluation where a study clinician is based, and to request that the clinician be contacted upon their arrival. With appropriate permission of the participant, whenever possible, records from all non-study medical providers related to untoward medical occurrences will be obtained and required data elements will be captured in the study database. All participants reporting an untoward medical occurrence will be followed clinically until the occurrence resolves (returns to baseline) or stabilizes.

Study site staff will document in source documents and in the study database all AEs reported by or observed in enrolled study participants regardless of severity and presumed relationship to study product. AE severity will be graded per the DAIDS Table for Grading Adult and Pediatric Adverse Events, Corrected Version 2.1, July 2017, and/or Addenda 1, 2 and 3 (Female Genital [Dated November 2007], Male Genital [Dated November 2007] and Rectal [Clarification Dated May 2012] Grading Tables for Use in Microbicide Studies).

Please note:

- Asymptomatic BV and asymptomatic candidiasis will not be reportable AEs;
- Fetal losses (e.g., spontaneous abortions, spontaneous fetal deaths, stillbirths) will
 not be reported as AEs (however, fetal loss data will be collected);

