9.4 Follow-up in Response to Observed Adverse Events

Grade 1 and Grade 2 Unrelated

In general, a participant who develops a Grade 1 AE as defined by the Division of AIDS Table for Grading the Severity of Adult and Pediatric Adverse Events, Corrected Version 2.1, July 2017, and/or Addenda 1, 2 and 3 (Female Genital [Dated November 2007], Male Genital [Dated November 2007] and Rectal [Clarification Dated May 2012] Grading Tables for Use in Microbicide Studies), regardless of relationship to study product, may continue product use. Participants who develop a Grade 2 AE that is judged by the IoR/designee to be unrelated to study product may also continue product use. If the IoR/designee opts to temporarily hold study product, the PSRT must be notified.

Grade 2 Related

For participants who develop a Grade 2 AE that is judged by the IoR/designee to be related to product, study product must be held and the IoR must consult with PSRT regarding continued study product use.

If a recurrence of the same Grade 2 AE judged to be related to study product recurs at any time during the study, study product must be temporarily held until the PSRT can be consulted regarding permanent discontinuation or other further management.

Grade 3 or Grade 4

For participants who develop a Grade 3 or 4 AE study product must be permanently discontinued and the PSRT notified.

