9.7 Criteria for Early Termination of Study Participation

Participants may voluntarily withdraw from the study for any reason at any time. IoRs/designees also may withdraw participants from the study to protect their safety and/or if they are unwilling or unable to comply with required study procedures, after consultation with the PSRT. Participants also may be withdrawn if NIAID, MTN, government or regulatory authorities, including the FDA and Office for Human Research Protections (OHRP), or site IRBs terminate the study prior to its planned end date. Every reasonable effort is made to complete a final evaluation of participants who withdraw or are withdrawn from the study prior to completing follow-up (see details regarding the Early Termination Visit in Section 7.5). Study staff members will record the reason(s) for all withdrawals in participants' study records.

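### A permanent product stop ends safety follow-up of a 4 mL or 16 mL dose already given

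*Protocol*

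**What the plan says.** Participants receive single doses of 4, 16 and 32 mL in the clinic from staff, two to six weeks apart (Protocol 6.1, 6.2). On permanent discontinuation, Section 7.5.3 reads: "Participants who permanently discontinue study product use for any reason (clinician-initiated or self-initiated) will be considered terminated from the study". It cancels further follow-up visits on the ground that staying in the study brings the participant nothing. It leaves two things: an Early Termination Visit that depends on the participant's agreement, and off-study follow-up of an adverse event (AE) that caused the stop.

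The related provisions are:

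- **24-hour visit (7.4.2):** "Safety laboratory tests and blood for PK will be collected from all participants at the 24 hour post-dosing visit". Table 14 requires CBC and AST/ALT/creatinine. A footnote refers to the SSP Manual "regarding the appropriate procedures to complete for an Early Termination Visit".
- **Other visits:** Table 13 (dosing) requires creatinine only. Tables 15 (48 hours) and 16 (Final Contact) list CBC and chemistries only if indicated. Appendix I agrees.
- **Final Contact (7.4.4):** it "will occur either in-person or by phone approximately two to six weeks after the third dosing visit (32 mL) of PC-1005 gel application".
- **AE collection (8.3.1):** the AE definition "is applied to all groups beginning at the time of enrollment through the termination visit".
- **Stop triggers:** Section 9.3 lists HIV infection, pregnancy, anogenital STI, PrEP or PEP, anticoagulants, CYP3A drugs and inability or unwillingness to comply. Section 9.4 adds: "For participants who develop a Grade 3 or 4 AE study product must be permanently discontinued and the PSRT notified".
- **Retention (9.7, 10.6, 10.7.3):** Section 9.7 says "Every reasonable effort is made to complete a final evaluation of participants who withdraw or are withdrawn from the study". Sections 10.6 and 10.7.3 promise efforts to complete scheduled evaluations and retain everyone enrolled.
- **SAP:** everyone dosed is analysed (3.1), under each volume actually received (3.2). A volume's AE window runs from dosing until the next volume is given (6.2).

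**The concern.** In a single-dose escalation, stopping product does not undo exposure. The reason given for ending follow-up therefore does not fit: the period after the last dose is exactly what the primary safety objective needs, and this is the first rectal use of the product.

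If the stop falls between a 4 mL or 16 mL dose and its remaining visits, two things cease to be required for that dose: the 24-hour visit (CBC, AST/ALT, 24-hour plasma sample), and collection of new AEs over the rest of the dose period. There is no Final Contact to fall back on, because that visit is tied to the third dose. The person still counts as a full unit in the volume's denominator, and SAP 6.2 does not say when the window closes if no next volume is given. For stops unrelated to an AE, a first Grade 2 or higher event after termination goes uncollected, which biases the primary proportion downwards.

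**Working it through.** **1. The plan's own figures.** Exact (Clopper-Pearson) 95% upper bounds at n = 12 are 26.46% for 0/12 and 38.48% for 1/12. Table 19 prints 26.4 and 38.4, so it reproduces apart from truncation in place of rounding.

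**2. Is there an exemption?** Neither document contains one:

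| Provision | Why it does not close the gap |
|---|---|
| Early Termination Visit (7.5.3) | Voluntary, no timing in the protocol, content left to the SSP Manual; one visit cannot cover weeks that follow it |
| Off-study AE follow-up (7.5.3); follow-up of reported occurrences (8.3.1) | Covers events already known, not new ones |
| Final evaluation (9.7) | One best-effort evaluation that refers back to 7.5 |
| Efforts in 10.6 and 10.7.3 | Pull against 7.5.3 but exempt no visit from it |
| Replacement (10.6, 10.7.3) | Discretionary; adds a new person and does not observe the one exposed |

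**3. Follow-up time lost per stop.** The dose period is 14 to 42 days.

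- Stop just after the 24-hour visit: 13/14 = 92.9% to 41/42 = 97.6% of the period has no required ascertainment of new AEs.
- Stop at the next pre-dose assessment: about 0%.
- Missing the 24-hour visit itself needs a stop in the first day, which is 1/42 = 2.4% to 1/14 = 7.1% of the period. It removes 1/12 = 8.3% of that volume's post-dose CBC and AST/ALT data (SAP 8.3), unless the Early Termination Visit recovers them.

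**4. Effect on the primary proportion.** Take one truncated participant among 12, stopped for a non-AE reason. Let p be the true rate and g (0 to 1) the share of first events falling after the stop. The expected observed proportion is p × (1 − g/12):

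| p | g = 0 | g = 1 |
|---|---|---|
| 5% | 5.0% | 4.6% |
| 10% | 10.0% | 9.2% |
| 25% | 25.0% | 22.9% |

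With 2 or 3 truncated and g = 1, 10% becomes 8.3% or 7.5%, and 25% becomes 20.8% or 18.8%.

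**5. A missed sole event.** The chance that this person's first event is missed is p × g, at most p. If nobody else has an event, 1/12 is reported as 0/12 and the upper bound falls from 38.4% to 26.4%. With g = 1 the chance of that, per stop, is p(1 − p)^11: 0.05 × 0.5688 = 2.8%, 0.10 × 0.3138 = 3.1%, 0.25 × 0.0422 = 1.1%. The maximum, at p = 1/12, is 3.2%.

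**6. Plasma PK.** SAP 9.2 needs at least three concentrations after Cmax to calculate ke. Post-dose samples by 24 hours are at 1, 2, 3, 4, 5–6 and 24 hours:

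| tmax | Values after Cmax, with 24 h | Without 24 h |
|---|---|---|
| 1 h | 5 | 4 |
| 2 h | 4 | 3 |
| 3 h | 3 | 2 |
| 4 h | 2 | 1 |

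The 24-hour sample decides the matter only at a tmax of about 3 hours. At 4 hours ke cannot be calculated by 24 hours either way, which is a limit of the SAP rule. After a stop for a CYP3A drug the sample may also be confounded.

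**The case against.** The best counter-argument is that the gap is narrow and the plan half-recognises it. In Section 10.6 the retention promise directly follows, and qualifies, the sentence about replacing people who permanently discontinue, so this could be read as an inconsistency to clarify. The SSP Manual may give the Early Termination Visit much of the 24-hour content. There is no required contact between the 24- or 48-hour visit and the next dosing visit, so many triggers will surface at the pre-dose assessment, where almost nothing is lost. Even participants who continue have their washout AEs reviewed essentially once, over a window that already varies threefold. A related Grade 2 event leads to a hold and consultation with the Protocol Safety Review Team, not automatic termination. Grade 3–4 stoppers already count as events, and a Grade 3 result from the scheduled 24-hour tests is known only after those samples are taken. Some unwilling participants would decline any contact. The safety analysis is descriptive.

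Most of this stands as a limit on size. It does not remove the rule. An aspiration in 10.6 does not override an explicit instruction to terminate, and a site reading both would not know which to follow. The Manual cannot be checked here, and even a full Early Termination Visit would not cover the weeks after it. A single review at the end of washout can capture events from the whole period; after early termination there is no such review.

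**Conclusion.** The concern holds. Section 7.5.3 ends required safety observation of a dose already given, and nothing in the protocol or SAP exempts the visits still due. The expected numerical effect is small: with one truncated non-AE stopper in 12, at most 0.4, 0.8 or 2.1 percentage points at true rates of 5%, 10% or 25%. The chance of turning a sole event into none is about 3% or less per stop. The loss for the individual ranges from about 0% to 98% of the dose period, depending on when the stop occurs.

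These figures are per stop, because the documents give no discontinuation rate. The share of events after the stop is assumed, and the laboratory and PK losses assume that the Early Termination Visit recovers nothing. The point concerns 4 mL and 16 mL: after 32 mL no product is left to stop, so Visit 9 should stand. The case for change is better safety ascertainment at low cost; no likely change to the trial's conclusion has been shown.

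**What to change.** Amend Section 7.5.3 to separate stopping product from ending safety observation. A participant who has been dosed, stops further product and has not withdrawn consent should:

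- complete the non-invasive parts of the 24-hour visit for that dose: CBC, AST/ALT/creatinine, plasma PK and AE review;
- have a Final Contact, by phone if preferred, 2–6 weeks after the last dose received, with all new AEs recorded until then, followed by termination.

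Rectal sampling and any assigned 48-hour visit become optional, done only if the participant is willing and the investigator judges them safe and interpretable. The criteria for stopping product do not change. In SAP 6.2, add a sentence closing the last received volume's window at that contact.

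The cost is a protocol amendment with IRB approval and registration (Protocol 13.1, 13.2), plus one already scheduled blood draw and one call for each participant who stops. No new visit type or mandatory endoscopy is needed. The downsides are a small extra burden on those participants and the need to flag late PK samples taken after prohibited drugs.
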